**B. PROCEDURE EXCLUSIONS/RULE-OUTS**

**1. POPULATIONS EXCLUDED FROM ALL PROCEDURES:**

- a) INABILITY TO GIVE INFORMED CONSENT (A DIMINISHED UNDERSTANDING OR COMPREHENSION);
- b) INABILITY TO TRAVEL TO OUTPATIENT FACILITY;
- c) PREGNANT WOMEN;
- d) PRISONERS; AND
- e) CHILDREN, UNDER THE AGE OF 16 YEARS OLD.

**2. RULE-OUTS FOR *VENOUS* PROCEDURE**

- a) ACTIVE TUBERCULOSIS;
- b) HISTORY OF CANCER (WITHIN THE PAST 5 YEARS);
  - i. ON A CASE-BY-CASE BASIS, PROVIDER MAY APPROVE PROCEDURE(S) FOR NON-AGGRESSIVE/NON-ACTIVE CASE(S).
- c) IDENTIFICATION OF NEW NODULES/MASSES PER CHEST X-RAY/CT SCAN REPORT THAT HAVE NOT BEEN NOTED AS STABLE.
  - i. DOCUMENTATION OF STABILITY MUST BE RECEIVED FOR CONFIRMATION PRIOR TO TREATMENT.
- d) ACTIVE INFECTION (PULMONARY OR OTHER);
- e) A HISTORY OF RECENT HOSPITALIZATION (REQUIRING MECHANICAL VENTILATION IN A PERIOD OF ONE MONTH BEFORE TREATMENT);
- f) END STAGE KIDNEY FAILURE;
- g) ACUTE HEART FAILURE; AND/OR
- h) OTHER CONDITION(S) THE PROVIDER OR PRINCIPAL INVESTIGATOR FEELS WOULD INTERFERE WITH TREATMENT PROTOCOLS.

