### 9b. Exclusion criteria

Exclusions from **ALL** Procedures:

- Populations
  - Inability to give informed consent (a diminished understanding or comprehension);
  - Inability to travel to Outpatient Facility;
  - Pregnant women;
  - Prisoners; and
  - Children, under the age of 16 years old
- Active Smoker - Active smoking prevalence has been estimated at:
  - Nationally: 17.8 %
  - Texas: 15.9 %
  - Dallas County: 15.3 %
  - Denton County: 10.1 %
  - Collin County: 9.7 %
- Currently diagnosed with cancer or have had cancer within the past 5 years.
  - Current cancer prevalence is estimated by the National Cancer Institute at 3.7% for males in Texas and 3.9% for females in Texas. National cancer cases were estimated in 2010 to be 13,772,000 nationally for a prevalence rate of 4.5% of the estimated national population of 309,300,000.
- Identification of new nodules/masses per chest x-ray/CT scan report that have not been noted as stable.
  - Documentation of stability must be received for confirmation prior to treatment.
- Active Infection (pulmonary or other);
- Active Tuberculosis
- A History of Recent Hospitalization (requiring mechanical ventilation in a period of one month before treatment);
- End Stage Kidney Failure;
- Acute Heart Failure; and/or
- Other Condition(s) the Provider or Principal Investigator feels would interfere with treatment protocols.

Rev\_2/5/16 Page 4 of 10

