**Research Protocol**  
**Lung Institute Dallas**

## 11. STUDY PROCEDURES

Informed Consent Form is obtained. Consent form must be complete, signed, and dated without forgeries or alterations. Information should be delivered in a manner in which the Patient and/or the patient's legal representative could reasonably be expected to understand.

A review of the patient's medical record will be conducted to approve for treatment. Approved treatment plans will be documented in the patient's electronic medical record. Medical records obtained from external providers will be kept in the patient's medical record and must include recent laboratory data, results of any outside office notes, chest x-ray results and any relevant information as required per treatment inclusions and exclusions protocol.

Prior to Bone Marrow aspiration, Adipose extraction, and Venous stem cell administration, the clinician will perform a physical assessment. Attached are the following Standard Operating Procedures (SOPs) for each type of cell therapy that Lung Institute provides to qualified candidates:

- Venous Procedure
- Adipose Extraction Procedure
- Bone Marrow Aspirate Procedure

Patient follow-up may be conducted at the Lung Institute facility or may be completed by telephone at 2 weeks, 3 months and 6 months post-treatment to measure adverse events and quality of life. Patient participation in these phone calls is voluntary. Data collected at these time points will be entered into password-protected database for data management and reporting. Patients will be issued a journal during their treatment to record quality of life indicators from the time they are discharged from the clinic until they are called for follow-up. This allows the patients to better recall how they felt/are feeling to better communicate progress during follow-up appointments/calls.

Patients will have pulmonary function testing 6 months post-treatment. This will be done at the Lung Institute facility, or by their primary care physician, or pulmonologist.

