#### **11a. Recruitment of participants**

Patients are included in treatment by self-referral. Patient coordinators conduct a series of questions with prospective patients to determine initial candidacy. If prospective patients are found to meet candidacy criteria, records are obtained to be reviewed by the mid-level provider and/or physician to determine final eligibility and approval for treatment.

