**DEFINITIONS:**

**A-ASC PROCEDURE/TREATMENT:** AN AUTOLOGOUS-ADULT STEM CELL MEDICAL PROCEDURE.

**CLINICAL STAFF:** A LICENSED PHYSICIAN OR PRACTITIONER, AND EMPLOYEE(S) WORKING BY DELEGATION THEREOF.

**EMPLOYEE (STAFF):** PERSON(S) EMPLOYED BY LUNG INSTITUTE (LI) AND/OR ITS ADMINISTRATOR AND MANAGING AFFILIATE REGENERATIVE MEDICINE SOLUTIONS (RMS). AN EMPLOYEE INCLUDES FULL-TIME, PART-TIME, TEMPORARY, VOLUNTEERS, TRAINEES, CONTRACTED/CONSULTING INDIVIDUALS, AND OTHER INDIVIDUALS WHOSE CONDUCT IS UNDER THE DIRECT CONTROL OF LI (WHETHER OR NOT THEY ARE PAID BY LI).

**EQUIPMENT:** A CLINICAL INSTRUMENT USED IN A CLINICAL SETTING.

**FACILITY:** A LUNG INSTITUTE (LI) PRACTICE LOCATION/CLINICAL SITE.

**PROVIDER/PRACTITIONER:** AN LI EMPLOYED PHYSICIAN, NURSE PRACTITIONER, OR ANY OTHER LICENSED CLINICAL STAFF MEMBER WHICH RENDERS CARE TO AN LI PATIENT; THIS INCLUDES PHYSICIAN EXTENDERS AND TEMPORARY PROVIDERS THAT HAVE BEEN APPROVED TO RENDER SERVICES AT AN LI FACILITY.

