**POLICY STATEMENT:**

THE LUNG INSTITUTE (LI) WILL SET AND MAINTAIN PRACTICE STANDARDS FOR ALL A-ASC TREATMENTS ADMINISTERED TO QUALIFYING PATIENTS DIAGNOSED WITH CHRONIC OBSTRUCTIVE PULMONARY DISEASE (COPD) OR INTERSTITIAL LUNG DISEASE (ILD), OR DIAGNOSED UNDER ONE OF THE VARIOUS ILD DISORDERS/DISEASES.

A-ASC TREATMENTS:

- a. VENOUS

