**3. RULE OUTS FOR *BONE MARROW* PROCEDURE**

- a) CURRENT BLOOD THINNER FOR ANY TYPE OF EXISTING HEART CONDITION;
- b) OSTEOPOROSIS;
- c) BILATERAL HIP REPLACEMENT;
- d) RADIATION OF PELVIS AREA (INCLUDING PROSTATE SEED IMPLANTS)
- e) ACTIVE TUBERCULOSIS;
- f) HISTORY OF CANCER (WITHIN THE PAST 5 YEARS);
  - i. ON A CASE-BY-CASE BASIS, PROVIDER MAY APPROVE PROCEDURE(S) FOR NON-AGGRESSIVE/NON-ACTIVE CASE.

- g) IDENTIFICATION OF NEW NODULES/MASSES PER CHEST X-RAY/CT SCAN REPORT THAT HAVE NOT BEEN NOTED AS STABLE.
  - i. DOCUMENTATION OF STABILITY MUST BE RECEIVED FOR CONFIRMATION PRIOR TO TREATMENT.
- h) ACTIVE INFECTION (PULMONARY OR OTHER);
- i) A HISTORY OF RECENT HOSPITALIZATION (REQUIRING MECHANICAL VENTILATION IN A PERIOD OF ONE MONTH BEFORE TREATMENT);
- j) END STAGE KIDNEY FAILURE;

10Mar2016 - version 2.0

LI-001

- k) ACUTE HEART FAILURE;
- l) UNCONTROLLED DIABETES;
- m) OTHER CONDITION(S) THE PROVIDER OR PRINCIPAL INVESTIGATOR FEELS WOULD INTERFERE WITH TREATMENT PROTOCOLS; AND/OR
- n) MEDICATION RULE-OUTS AS FOLLOWS:
  - i. MUST BE OFF ANTICOAGULATION DRUGS AND OTHER MEDICATIONS AND/OR SUBSTANCES THAT CAUSE BLEEDING. (MUST BE HELD FOR AN ALLOTTED TIME WITH PRIOR APPROVAL FROM PCP/PRESCRIBING PHYSICIAN-SPECIFIC HOLD TIMES ARE SUBJECT TO MEDICATION/SUBSTANCE TYPE.)
  - ii. METHOTREXATE (IF UNABLE TO HOLD FOR 1 WEEK PRIOR TO TREATMENT)

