### **ATTACHMENT(S):**

**A-1:** VENOUS PROCEDURE (CLINICAL - SOP)

**A-2:** BONE MARROW ASPIRATE PROCEDURE (CLINICAL - SOP)

**A-3:** DISCHARGE TREATMENT DAY PROCEDURE (CLINICAL-

**SOP) A-4:** OFFICE MANAGER PROCEDURE (CLINICAL-SOP)

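### Section 9b excludes recent cancer without exception, but clinic policy CL-005 lets a provider waive that exclusion, and no explicit clause switches the waiver off for study patients

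*Combined protocol and SAP*

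**What the plan says.** Section 9 of the protocol opens by saying that its inclusion and exclusion criteria settle who may enter the study and serve participants' safety. In Section 9b, the list covering all procedures excludes anyone "Currently diagnosed with cancer or have had cancer within the past 5 years". No exception follows.

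CL-005, the clinic policy bundled with the protocol, describes itself as setting "PRACTICE STANDARDS FOR ALL A-ASC TREATMENTS ADMINISTERED TO QUALIFYING PATIENTS" who have COPD or ILD. Part B.2 (venous procedure) makes cancer history in the same five years a rule-out, then adds at item b(i): "ON A CASE-BY-CASE BASIS, PROVIDER MAY APPROVE PROCEDURE(S) FOR NON-AGGRESSIVE/NON-ACTIVE CASE(S". Part B.3 (bone marrow procedure) does the same at item f(i): "ON A CASE-BY-CASE BASIS, PROVIDER MAY APPROVE PROCEDURE(S) FOR NON-AGGRESSIVE/NON-ACTIVE CASE".

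Under Section 11a, a prospective patient's records are "reviewed by the mid-level provider and/or physician to determine final eligibility and approval for treatment". CL-005 defines the provider who holds the waiver as "AN LI EMPLOYED PHYSICIAN, NURSE PRACTITIONER, OR ANY OTHER LICENSED CLINICAL STAFF MEMBER" rendering care to its patients, so the people who decide study eligibility fall within that definition.

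**The concern.** The first research question in Section 4 is whether collecting and giving the cells is safe. Section 13 lists transfer of an undiagnosed cancer among the risks and mentions tumor induction. Cancer history is therefore a safety criterion that decides who is exposed.

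Take a patient with an inactive, non-aggressive cancer three years ago. Section 9b excludes this patient. CL-005 allows a provider to approve the same patient. If the provider has CL-005 in hand, the written permission is there and nothing in that policy says it stops at the study's door. At stake are the exposure of a patient whom the protocol meant to protect, and a safety population that may not match the stated criteria.

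**Working it through.** No arithmetic on power or effect size applies. The check compares the two texts and asks whether CL-005 reaches study patients.

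**1. Is the Section 9b exclusion unconditional?** Yes. Its provider-judgement item can only add exclusions. Where the protocol wants discretion it writes it out: case-by-case exceptions appear for BMI and for cardiac history under the adipose procedure, but not for cancer.

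**2. How far do the lists differ?** Leaving aside the excluded populations, the Section 9b list for all procedures has 9 items. Set against the venous list (8 items) and the 8 corresponding items of the bone marrow list in CL-005:

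| Section 9b item | In both CL-005 lists |
|---|---|
| New nodules or masses; active infection; tuberculosis; recent ventilated hospitalization; end-stage kidney failure; acute heart failure; other conditions (7 items) | Same content |
| Cancer (1 item) | Same five-year window, waiver added; current diagnosis not named separately |
| Active smoker (1 item) | Not listed |

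7 + 1 + 1 = 9. The waiver appears in 2 of 2 CL-005 procedure lists and 0 times in Section 9b.

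**3. Does CL-005 reach study patients?** The protocol body never names it, so the link is indirect, but several strands point the same way:
- CL-005 covers all of the clinic's stem cell treatments, and its rule-out lists refer to the principal investigator.
- Section 11 of the protocol states: "Attached are the following Standard Operating Procedures (SOPs) for each type of cell therapy". The attachments to CL-005 include the venous SOP and the "BONE MARROW ASPIRATE PROCEDURE (CLINICAL - SOP". Both SOPs cite CL-005 as a related document.
- Section 2a says that every patient of the clinic is treated under the same protocols.
- Section 11 sends record review to a treatment inclusion and exclusion protocol that it does not identify. That could mean Section 9 or CL-005.

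**4. Does any text rank the two?** Section 9's opening assigns study entry to Section 9, which favours 9b. The IRB's notification terms require approval before changes are implemented and bar the investigator from changing the research without it. Neither is an explicit precedence clause, and neither mentions CL-005. The dates do not settle it: the protocol pages are Rev 2/5/16, while CL-005 was last revised 3/8/2016 and its pages are marked 10Mar2016, version 2.0. No text says the later document replaces the earlier one.

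**5. Can the number of patients be estimated?** No. Section 9b gives general-population cancer prevalence (3.7% of males and 3.9% of females in Texas). It does not give the share of this lung-disease population with cancer in the past five years, the share that would count as non-aggressive or non-active, or the share a provider would approve.

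**The case against.** The strongest reply is that Section 9 already answers the question. Its opening sentence gives it authority over study entry, whereas CL-005 is a general practice policy for all departments and every clinic location. The IRB terms also weigh against a clinic policy loosening a protocol criterion. This stands in large part: it is a good reason to read 9b as governing. It does not remove the written permission that CL-005 gives to the people who decide eligibility.

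A second reply is that the waiver is permissive. Both documents make cancer within five years a rule-out by default, and a provider who declines the waiver for study patients complies with both. This also stands. A reader might infer that the two documents give opposite instructions; they do not, because CL-005 never requires approval.

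Third, passages were removed before review, including material next to the IRB terms. A governing statement may exist there. This limits the point to the supplied text and lowers confidence.

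A reader might also infer that excluded patients were in fact treated, or that the FEV1 comparison is distorted. The documents show no use of the waiver and nothing from which an effect on FEV1 could be derived.

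**Conclusion.** The point holds as a mismatch that should be corrected. Section 9b excludes recent cancer without exception and Section 9 claims authority over study entry, yet a policy covering the same treatments and the same decision-makers offers a discretionary waiver in the same window. Without an explicit clause disabling it, a provider relying on CL-005 could treat a study patient whom the protocol excludes on safety grounds.

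Its extent in the text is two waiver items, one for each procedure that CL-005 gives rule-outs for. Its extent in patients is unknown and could be zero. The conclusion assumes that CL-005 is in use for study patients, which the bundling, shared SOPs and Section 2a support but do not prove, and that no removed page supplies a precedence rule. Confidence is moderate.

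**What to change.** Add a statement to the protocol that Section 9 governs eligibility of study patients and that the cancer waiver in CL-005 B.2(b)(i) and B.3(f)(i) does not apply to them. This needs IRB approval before implementation. The same statement settles active smoking, which Section 9b excludes and CL-005 B.1 to B.3 do not list. A short cross-reference at the two CL-005 items would help but is secondary. It should be limited to study patients, since the policy also serves patients outside the study.

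Check the records of patients already treated for any use of the waiver; at the planned sample size (Section 12a) that is at most 200 charts. Identify any such patients in the safety listing, and report significant deviations to the IRB within the five business days from discovery that its terms set.

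If the sponsor wants the waiver in the study, the route is an IRB-approved amendment of Section 9b with defined criteria that rule out any active cancer, repeated in the same words in CL-005.

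The cost is a short protocol amendment and a chart check. The downside is that patients who would have been approved under the waiver are not treated in the study; their number is unknown.

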**3. RULE OUTS FOR *BONE MARROW* PROCEDURE**

- a) CURRENT BLOOD THINNER FOR ANY TYPE OF EXISTING HEART CONDITION;
- b) OSTEOPOROSIS;
- c) BILATERAL HIP REPLACEMENT;
- d) RADIATION OF PELVIS AREA (INCLUDING PROSTATE SEED IMPLANTS)
- e) ACTIVE TUBERCULOSIS;
- f) HISTORY OF CANCER (WITHIN THE PAST 5 YEARS);
  - i. ON A CASE-BY-CASE BASIS, PROVIDER MAY APPROVE PROCEDURE(S) FOR NON-AGGRESSIVE/NON-ACTIVE CASE.

- g) IDENTIFICATION OF NEW NODULES/MASSES PER CHEST X-RAY/CT SCAN REPORT THAT HAVE NOT BEEN NOTED AS STABLE.
  - i. DOCUMENTATION OF STABILITY MUST BE RECEIVED FOR CONFIRMATION PRIOR TO TREATMENT.
- h) ACTIVE INFECTION (PULMONARY OR OTHER);
- i) A HISTORY OF RECENT HOSPITALIZATION (REQUIRING MECHANICAL VENTILATION IN A PERIOD OF ONE MONTH BEFORE TREATMENT);
- j) END STAGE KIDNEY FAILURE;

10Mar2016 - version 2.0

LI-001

- k) ACUTE HEART FAILURE;
- l) UNCONTROLLED DIABETES;
- m) OTHER CONDITION(S) THE PROVIDER OR PRINCIPAL INVESTIGATOR FEELS WOULD INTERFERE WITH TREATMENT PROTOCOLS; AND/OR
- n) MEDICATION RULE-OUTS AS FOLLOWS:
  - i. MUST BE OFF ANTICOAGULATION DRUGS AND OTHER MEDICATIONS AND/OR SUBSTANCES THAT CAUSE BLEEDING. (MUST BE HELD FOR AN ALLOTTED TIME WITH PRIOR APPROVAL FROM PCP/PRESCRIBING PHYSICIAN-SPECIFIC HOLD TIMES ARE SUBJECT TO MEDICATION/SUBSTANCE TYPE.)
  - ii. METHOTREXATE (IF UNABLE TO HOLD FOR 1 WEEK PRIOR TO TREATMENT)

**C. ELEMENTS OF INFORMED CONSENT**

1. A SIGNED CONSENT FORM WITH THE FOLLOWING ELEMENTS CONSTITUTES PRIMA FACIE EVIDENCE THAT THE PATIENT OR THE PATIENT'S LEGAL REPRESENTATIVE GAVE INFORMED CONSENT TO THE HEALTH CARE PROVIDER.
2. INFORMATION SHOULD BE DELIVERED IN A MANNER IN WHICH THE PATIENT AND/OR THE PATIENT'S LEGAL REPRESENTATIVE COULD REASONABLY BE EXPECTED TO UNDERSTAND.
3. PATIENT MUST BE PROVIDED A MINIMUM OF:
  - a) THE NATURE AND CHARACTER OF THE PROPOSED TREATMENT;
  - b) THE ANTICIPATED RESULTS OF THE PROPOSED TREATMENT, WITH 'NO GUARANTEES' MADE BY LI;
  - c) ANY AVAILABLE ALTERNATIVE FORMS OF TREATMENT INCLUDING NON-TREATMENT;
  - d) THE RECOGNIZED RISKS AND COMPLICATIONS; AND
  - e) THE ANTICIPATED BENEFITS INVOLVED IN THE TREATMENT.

**D. PATIENT PAPERWORK & DISCLOSURES**

1. LI PROVIDERS WILL PRACTICE APPROPRIATELY UNDER THEIR LICENSED AND/OR THEIR CERTIFIED SCOPE.
2. DELEGATION OF CLINICAL FUNCTIONS ARE ONLY PERMITTED TO TRAINED AND QUALIFIED INDIVIDUALS.

**E. ATTENDING PROVIDER**

1. ONLY PROVIDERS WHO'S CREDENTIALS HAVE BEEN VERIFIED AND HAVE BEEN GRANTED PRIVILEGING MAY RENDER TREATMENT AND SERVICES AT LI FACILITIES. (REFER TO PROVIDER QUALIFICATIONS & PRIVILEGING P&P No.: HR-001)
  - a) THE TREATING LICENSED PROFESSIONAL(S)
    - i. PHYSICIAN
    - ii. NURSE PRACTITIONER (ARNP/CRNP/APRN; APN)
    - iii. PHYSICIAN ASSISTANT (PA)
    - iv. REGISTERED NURSE (RN)
    - v. LICENSED PRACTICAL NURSE (LPN/LVN)
    - vi. MEDICAL ASSISTANT (CMA/MA)
2. LI PROVIDERS WILL PRACTICE APPROPRIATELY UNDER THEIR VALID LICENSE(S) AND/OR THEIR CERTIFIED SCOPE OF SERVICES.
  - a) DELEGATION OF CLINICAL FUNCTIONS ARE PERMITTED TO INDIVIDUALS QUALIFIED AND/OR TRAINED TO PERFORM SAID DELEGATED FUNCTIONS.

3. IT IS THE RESPONSIBILITY OF THE ATTENDING PROVIDER TO ASSURE THAT THE PATIENT AND/OR THE LEGAL REPRESENTATIVE HAS BEEN INFORMED OF RISKS, BENEFITS, AND ALTERNATIVES OF PROCEDURE AND HAS CONSENTED TO TREATMENT WITHOUT COERCION, GIVING THEIR INFORMED CONSENT, AND TO DOCUMENT THE PROCESS IN PATIENT'S MEDICAL RECORD.
4. PROCUREMENT OF CELLS ARE CONDUCTED USING STERILE TECHNIQUES AND UNIVERSAL PRECAUTIONS TO MINIMIZE RISK OF CONTAMINATION AND INFECTION. (REFER TO MEDICAL EQUIPMENT MAINTENANCE AND MANAGEMENT P&P No.: CL-001)
5. TREATMENT PROTOCOLS INCLUDES A CLEAR, TIMELY, AND EFFECTIVE PLAN FOR REPORTING ADVERSE OCCURRENCES. (REFER TO INCIDENT REPORTING P&P No.: OP-004)

10Mar2016 - version 2.0

## **F. LIFE-THREATENING EMERGENCIES**

LI-001

1. IMPLIED CONSENT EXISTS FOR ALL LIFE-THREATENING EMERGENCIES. HEALTH CARE PROVIDERS WHO ACT IN GOOD FAITH RECEIVE IMMUNITY WHEN RENDERING EMERGENCY CARE. IF A LIFE-THREATENING CARE EMERGENCY EXISTS AND THE PATIENT IS NOT CAPABLE OF GIVING INFORMED CONSENT OR A LEGALLY AUTHORIZED PERSON IS UNAVAILABLE, CONSENT WILL BE IMPLIED. A LIFE-THREATENING EMERGENCY IMPLIES THAT IMMEDIATE TREATMENT IS NECESSARY TO PRESERVE LIFE, OR TO PREVENT SERIOUS DETERIORATION OR AGGRAVATION OF THE PATIENT'S CONDITION. IMPLIED CONSENT IS FOR TREATMENT OF THE EMERGENCY ONLY.
  - a) A MINIMUM OF ONE PROVIDER IS TRAINED AND CERTIFIED FOR EMERGENCY RESPONSE AND IS ON-SITE DURING THE RENDERING OF PATIENT TREATMENT(S):
    - i. BASIC LIFE SUPPORT (BLS) CERTIFICATION/CPR CERTIFICATION
    - ii. ADVANCED CARDIO LIFE SUPPORT (ACLS) CERTIFICATION

## **G. POST TREATMENT**

1. PATIENTS ARE PRESCRIBED AND/OR RECOMMENDED TO FOLLOW A COMPREHENSIVE FOLLOW-UP PROTOCOL, INCLUDING THE FOLLOWING:
  - a) NEBULIZER AND/OR NEBULIZER SOLUTIONS;
  - b) SUPPLEMENTS;
  - c) PULMONARY REHABILITATION RECOMMENDED TO BE ORDERED BY PRIMARY CARE PHYSICIAN OR PULMONOLOGIST; AND
  - d) INCENTIVE SPIROMETER AND INSTRUCTIONS FOR USE.

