## **2a. Situating the Researcher**

[name] is a doctorally-prepared Family Nurse Practitioner certified by the American Nurses Credentialing Center and licensed to practice in the state of Texas. A member of the Southern Nursing Research Association, [name] has experience designing and conducting qualitative and quantitative research and mixed-methods studies. Her doctoral dissertation was a qualitative study involving a marginalized population of drug-addicted women ([name], 2013). She has also done pilot work on a population of incarcerated women using quantitative methods. [name] has a current manuscript pending review on using the interpretive phenomenological inquiry method for qualitative research. [name] is well-experienced in the protection of human research subjects. She is an expert in the promoting rigor in qualitative research design and situating its importance in medical research.

[name] is a nationally certified and practicing Family Nurse Practitioner. In addition to her research role, [name] will be the primary clinician at the research site, providing physical assessments, reviewing patient medical records and formulating the patient plan of care. Because each patient of the Lung Institute is treated using the same protocols (there are no control groups), this minimizes the conflict of interest, randomization and blinding that must occur with experimental studies.

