## **4. RESEARCH QUESTIONS**

The research questions to be informed by this investigation are as follows:

1. Is the collection and administration of autologous stem cells for the treatment of chronic lung disease safe?
2. Does treatment with autologous stem cells for chronic lung disease improve measurements of pulmonary function (specifically FEV1)?
3. Does treatment with autologous stem cells for chronic lung disease improve the patient's perceived quality of life?

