### **12b. Statistical methods**

For the quantitative, descriptive arm of this study, sample characteristics will be collected to include age, sex and diagnosis. Pre- and post-treatment FEV1 measurements will be collected on each patient and evaluated by simple measures of central tendency (mean, median and mode). Sufficient descriptive data will be collected and reported to encourage replication of our study.

For the qualitative, anecdotal arm of the study, Lung Institute utilizes CCQ, the Clinical COPD Questionnaire to document patient's perceptions on improved quality of life. The information will be collected and interpreted by evaluating for common themes within the anecdotes. As a note regarding the rigor of qualitative research: is important in qualitative research to ensure that the study is credible and trustworthy (Smith, Flowers and Larkin, 2009). A number of guidelines for assessing this quality look toward establishing credibility. Psychologist Lucy Yardley's work in 2000 provides the principles for assessing the quality of qualitative research and how the interpretive phenomenological method can address them. First, the study must provide good *sensitivity to context*. In this study, the immersion in the clinic through field experience, the existing literature on COPD and stem cell treatment, and the anecdotes obtained

Rev\_2/5/16 Page 7 of 10

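### The six-month FEV1 and CCQ change reflects a whole treatment package, but the plan frames it as the result of stem cells and has no stated plan to record uptake of the other components

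*Combined protocol and SAP*

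**What the plan says.** CL-005 section G sets the post-treatment regimen: "PATIENTS ARE PRESCRIBED AND/OR RECOMMENDED TO FOLLOW A COMPREHENSIVE FOLLOW-UP PROTOCOL, INCLUDING THE FOLLOWING". Its four items are "NEBULIZER AND/OR NEBULIZER SOLUTIONS", supplements, "PULMONARY REHABILITATION RECOMMENDED TO BE ORDERED BY PRIMARY CARE PHYSICIAN OR PULMONOLOGIST", and "INCENTIVE SPIROMETER AND INSTRUCTIONS FOR USE". No subset of patients is named, and Section 2a of the protocol says that "each patient of the Lung Institute is treated using the same protocols (there are no control groups").

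The comparison is within patient, pre-treatment against six-month FEV1 (Section 6), with the CCQ for quality of life (Section 12b). Section 4 asks: "Does treatment with autologous stem cells for chronic lung disease improve measurements of pulmonary function (specifically FEV1")? Section 5a sets a null of no FEV1 improvement at six months against a gain of 5 to 10% or more following cell treatment. Section 6 aims to generalise an improvement to everyone treated this way.

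On data, Section 12b says that "sample characteristics will be collected to include age, sex and diagnosis". Section 11 schedules contacts at "2 weeks, 3 months and 6 months post-treatment to measure adverse events and quality of life". Section 12b summarises FEV1 by measures of central tendency and describes no stratification or adjustment.

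**The concern.** The clinic's own procedures put several other measures into the interval over which change is measured. Rehabilitation and nebulised treatment could plausibly alter activity, CCQ answers and possibly FEV1. The protocol also hopes for changes in medication: Sections 1 and 13 list doing without rescue or bronchodilator inhalers, and Section 13 adds prednisone. Such changes could move FEV1 in either direction.

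If the six-month result is reported in the terms of Sections 4, 5a and 6, a reader will credit the cells with whatever the package produced. If uptake is not asked about during follow-up, the report cannot even say how many patients had rehabilitation. Outside physicians order it, so the clinic's records will not show it by default. A site wishing to replicate the study, which Section 12b says it wants to encourage, would not know what had been given.

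**Working it through.** **Where uptake might be recorded.**

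- Baseline characteristics (Section 12b): age, sex and diagnosis are named. The list is open, but no co-intervention is on it.
- Follow-up contacts (Section 11): the stated purpose is adverse events and quality of life.
- Patient journal (Section 11): quality-of-life indicators.
- Six-month visit (CL-005 section H): evaluation, labs, lung function, oximetry and walk test. The content of the evaluation is not itemised.
- EMR steps (Venous SOP step 25, Bone Marrow SOP step 43, Discharge SOP step 20): what was done on treatment days, not later use.
- Medication before treatment: reviewed in step 2 of the Venous and Bone Marrow SOPs and in the venous history (step 14). It is not in the bone marrow history list (step 12). No later reassessment is described.

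None of these plans to capture uptake or medication change over the six months.

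**Why the single arm is the root cause.** Expected mean change = cell effect + contribution of the other measures + everything else that changes over six months. One arm gives one equation, and the terms cannot be separated. Knowing uptake does not add a control group.

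**The plan's own figures.** The documents give no effect of these measures on FEV1 and no uptake. The sample size of 200 has no stated inputs, so it cannot be reproduced. With n = (SD × (1.960 + 0.842) / 5)², a 5% change at 80% power and two-sided 5% needs 32, 71, 126, 197 or 283 patients for an assumed SD of percent change of 10, 15, 20, 25 or 30.

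**Illustration of size (all inputs assumed).** Contribution = uptake × effect.

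- Lowest: 0.25 × 0 = 0 points.
- Highest: 0.75 × 5 = 3.75 points.

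Now suppose the cell effect is zero, uptake is 50% and the co-intervention effect is 5%, so b = 0.50 × 5 = 2.5 points. With n = 200 and se = SD/√200, a paired two-sided 5% test rejects no change with probability Φ(b/se − 1.96) + Φ(−b/se − 1.96):

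| Assumed SD | se | b/se | Probability |
|---|---|---|---|
| 15 | 1.06 | 2.36 | 0.65 |
| 20 | 1.41 | 1.77 | 0.42 |
| 25 | 1.77 | 1.41 | 0.29 |

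If the co-intervention effect is zero, the probability is 0.05. The contribution b does not shrink as n grows. At SD 20 the rejection probability rises from 0.24 with 100 patients to 0.42 with 200. Section 12b plans no test, so this shows only how readily Section 5a's null could be rejected without any cell effect.

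**What an uptake table could show.** With all 200 patients followed and assumed SD 15 to 25, the 95% half-widths are 1.96 × SD/√n₀ for the non-user mean and 1.96 × SD × √(1/n₀ + 1/n₁) for the difference, where n₀ is non-users and n₁ users:

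| Uptake | Non-users | Non-user mean | User minus non-user |
|---|---|---|---|
| 50% | 100 | ±2.9 to 4.9 | ±4.2 to 6.9 |
| 75% | 50 | ±4.2 to 6.9 | ±4.8 to 8.0 |
| 90% | 20 | ±6.6 to 11.0 | ±6.9 to 11.5 |
| 100% | 0 | none | none |

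The table can describe the cohort. It cannot isolate a cell effect, and at high uptake it is very imprecise.

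**The case against.** The strongest reply is that uptake data would not repair the study. Rehabilitation attendance depends on motivation, access, severity and an outside physician's order. Attendance and medication change also occur after treatment and may themselves depend on how the patient is doing. A user versus non-user table is therefore confounded. Calls are voluntary (Section 11) with two attempts each (CL-005 section H), so uptake data will be missing, probably not at random. All of this stands, and it limits the checklist to description.

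Four stronger readings are tempting, but the documents do not support them.

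- A reader might infer that the effects cannot be separated because uptake is unrecorded. The cause is the absence of a control group (Sections 2a and 11b).
- A reader might infer that every patient newly starts all four measures. CL-005 allows either a prescription or a recommendation and does not say that the measures are new to the patient.
- A reader might infer that Section 12b credits the change to cells. It contains only descriptive summaries, and Section 6 calls this arm non-experimental and descriptive. The attribution comes from Section 4's question, from Section 5a, which names cell treatment as the only exposure, and from Section 6's aim to generalise.
- A reader might infer that uptake is certainly recorded nowhere. The quality-of-life questionnaire is cited as attached but was not in the text available, and no call script is shown. The stated purpose of the calls makes an uptake item unlikely but does not exclude it.

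The descriptive label does not answer the point, because the plan also asks whether cells improve FEV1 and, in Section 12b, says it will inform the public and the medical community on efficacy.

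**Conclusion.** The point stands in limited form and should be acted on. The pre-post change in FEV1 and CCQ is change after a package. On venous treatment days that package also includes nebulised glutathione (Venous SOP step 22, Discharge SOP step 12). The plan's questions, primary hypothesis and generalising aim present the change as following from cells alone, and no available section plans to record uptake of the post-treatment measures or medication change. Conclusions drawn as framed would be unsound whatever the uptake turns out to be.

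The size of any co-intervention contribution is unknown. The range of 0 to 3.75 percentage points rests wholly on an assumed uptake of 25-75% and an assumed effect of 0-5%, and it treats four different measures as one. It must include zero, because nothing in the documents shows that these measures change FEV1. For the CCQ the documents give no basis for a figure.

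**What to change.** 1. **Wording.** In Sections 4, 5a and 6, and in any report, describe the result as change after the whole treatment package, and list its components. Do not describe it as the effect of stem cells. This is needed even if uptake proves universal.
2. **Data.** Add a short checklist to the 2-week, 3-month (12 weeks in CL-005 section H) and 6-month contacts: rehabilitation attended (yes/no, number of sessions), nebulizer solutions, supplements, incentive spirometer, and any change in inhaled or oral lung medication since baseline. Record prior use of each at baseline, for both the venous and bone marrow routes.
3. **Section 12b.** Report uptake with the number of patients answering, and FEV1 and CCQ change with and without rehabilitation and with and without a medication change. Label this descriptive only. State that the groups are self-selected and defined after treatment, that calls are voluntary so data will be missing, and that non-user groups may be small.

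The cost is a few questions per contact, one table and revised wording, with no change to treatment, visits or sample size. The downside is slightly longer calls and imprecise subgroups. Attribution to the cells themselves would need a concurrent control group given the same follow-up regimen, which this change does not supply.
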